10.1 LOSS OF CAPACITY FOLLOWING INFORMED CONSENT

Where valid informed consent is obtained from the participant and the participant subsequently becomes unable to provide ongoing informed consent by virtue of physical or mental incapacity, the consent previously given when capable remains legally valid.

Participants who lose capacity after informed consent has been obtained will continue with protocol treatment and assessments in consultation with the site Principal Investigator and the participant's carer / family with the participant's best interests foremost in the decision-making process. Ongoing collection of safety and follow-up

data will continue via the clinical care team for inclusion in the trial analysis in order to preserve the integrity of the trial's intention to treat analysis and to fulfil regulatory requirements specifically for pharmacovigilance purposes.

10.2 COLLECTION AND USE OF FULL PARTICIPANT NAME

Full participant name will be present on Informed Consent Documents and Contact Details Forms (required in order to send participant the trial questionnaires). This information will be stored securely at the trial site separate to all other STERLING-PMR trial data.

Full participant name will also be required on the reply slip that potential participants may return to the site in order to arrange the screening-suitability discussion.

11 REGISTRATION AND RANDOMISATION

Recruitment into the study is classed as a two-step process involving an initial registration of all potential participants, followed by randomisation for eligible participants.

11.1 REGISTRATION

Following confirmation of written informed consent, participants will be registered into the trial as soon as possible by an authorised member of the site research staff, as detailed on the Authorised Personnel Log. Informed consent for entry into the trial must be obtained prior to registration. Registration will be performed centrally using the automated web-based registration and randomisation system.

The person registering the participant must have the following information available at the time of accessing registration system:

- Personal authorisation codes and PIN;
- Name of study research site and site code;
- Participant details, including initials, biological sex, date of birth
- Confirmation of written informed consent, and date

All participants will be allocated a unique trial identification number after they have been registered.

Web address for 24-hour randomisation: <https://lictr.leeds.ac.uk/webrand/>

After trial registration the site research team will:

- Record the participant details on the STERLING Participant ID Log in the Investigator Site File
- Add the unique participant ID number to all CRFs
- Return an electronic copy of the completed consent form to CTRU via secure file transfer
- Ensure that participants are notified of their next appointment dates (e.g. chest x-ray, baseline assessment).

Following registration, CTRU will send an automated email to the site research team to confirm that a participant has been registered. This is to be checked by the participating site to ensure the information is correct.

11.2 CONFIRMATION OF ELIGIBILITY

After the participant has provided written informed consent and prior to the baseline assessments each participant will be assessed for their suitability for treatment. Please see Section 14.4 for details.

A maximum of 6 weeks will be permitted between registration and randomisation. During this time participants will continue with standard of care treatment.

11.3 RANDOMISATION

Randomisation will be a 1:1 allocation ratio to receive either Usual Care (steroid taper) Alone or Usual Care plus DMARD. Randomisation will be based on a minimisation algorithm with random component to ensure treatment groups are well-balanced for the following participant characteristics:

- site;
- number of previous relapses
- biological sex;
- prednisolone dose equivalent prior to last relapse (5mg or less, greater than 5mg) (see Appendix X for details of conversions from other glucocorticoids).

Randomisation process and timing

Participants who have previously been registered and have confirmation of eligibility will be randomised into the trial by an authorised member of the site research staff, as detailed on the Authorised Personnel Log. Randomisation will be performed centrally using the same CTRU automated web-based system as was used during registration and the same site code, authorisation code and PIN will be required. The baseline assessments and questionnaires should be completed BEFORE the participant is randomised.

The following information will be required whilst accessing the automated web-based system:

- site
- number of previous relapses
- biological sex
- prednisolone dose equivalent prior to last relapse (5mg or less, greater than 5mg)
- confirmation of participant's eligibility for the trial
- confirmation of informed consent
- confirmation of completion of baseline participant questionnaires

Web address for 24-hour randomisation: <https://lictr.leeds.ac.uk/webrand/>

Once randomisation is complete, the system will allocate a treatment arm for the participant and inform the user of the allocation.

The CTRU will send an automated email confirming participant randomisation and confirming the treatment allocation to the:

- site research team and
- site pharmacy

Site Research Team Post-Randomisation Activities

- Check automated email from CTRU to ensure participant information is correct e.g. initials, date of birth
- Update the participant's record on the STERLING Participant ID Log by adding details of the treatment allocation
- Return a copy of the completed participant contact details forms to CTRU
- Provide the participant with a Trial ID card and inform them that it should be carried at all times and presented to medical staff should they be admitted to hospital during their time in the trial or should they visit their GP. They will also discuss with the participant the situations in which it would be most appropriate to seek support from the site research team and the situations where it is more appropriate to approach their GP for advice.
- Notify the participant's GP of their participation in the trial using the appropriate approved STERLING GP Letter.
- Actions specific to participants randomised to receive Usual Care plus DMARD:
 - Agree with the participant what day of the week they will take their methotrexate. Prescribe an initial 6-week supply of methotrexate with folic acid following local procedures. It is the PI's responsibility to ensure that participants are counselled about the importance of how and when to take their methotrexate and folic acid. To ensure that participants receive up to date counselling and the same safety procedures as participants in routine care, participants will be provided with written participant information materials that would be provided for participants starting a DMARD in routine care, for example booklets produced by the independent charity Versus Arthritis, to supplement the verbal information given.
 - Issue paper DMARD monitoring blood tests laboratory request forms for the duration of the initial methotrexate prescription, with clear instructions for the participant about the time windows during which each test must be done, and the options they have for the blood draw (e.g. by appointment with their GP practice, or by visiting the site by appointment or drop-in, or a local pathology clinic according to local procedures). The participant will need to arrange their own blood tests.
 - Specifically remind the participant that if they develop an intercurrent infection they may need to stop their DMARD (but continue steroid) and inform the hospital team for advice on when the DMARD can be re-started.

Site Pharmacy Team Post-randomisation Activities:

- Record the participant details on the STERLING Participant ID Log in the Investigator Site File, including treatment allocation (applies to participants from both arms).

- Participants randomised to receive Usual Care plus DMARD:
 - Dispense prescribed supply of methotrexate and folic acid.
 - Apply trial specific labels to packaging of methotrexate
 - Check the participant's (and/or carers', if relevant) understanding about how and when to take methotrexate. Check that they are aware that methotrexate is a WEEKLY medication.

12 TRIAL MEDICINAL PRODUCT MANAGEMENT

12.1 Pharmacy Registration and Set-Up

A designated Pharmacist who takes overall responsibility for all pharmacy aspects of the trial must be identified and will be assigned as the Lead Pharmacist. This person will be listed on the main site Authorised Personnel Log and must sign the Lead Pharmacist Declaration. CTRU will provide participating pharmacies with a Pharmacy Site File (PSF). All STERLING trial related documentation must be retained in the PSF (or a file note documenting its location). When all approvals and essential documents are in place CTRU will formally notify the site and pharmacy that potential trial participants can be approached.

12.2 Investigational Medicinal Product (IMP) Definition

Within the trial, the following are classed as IMPs:

- methotrexate
- leflunomide

12.3 IMP Composition

Methotrexate

Composition: Oral tablets containing 2.5 mg methotrexate (AUS Variation: or 10mg of methotrexate)

Leflunomide

Composition: Oral tablets containing either 10mg or 20mg of leflunomide

12.4 IMP Supply

Both methotrexate and leflunomide are licensed in the UK and generic 'off the shelf' site supplies will be used. There is no requirement to ring-fence either methotrexate or leflunomide for the STERLING trial.

12.5 IMP Storage and Handling

For details on storage and handling please refer to the most recent version of the specific manufacturer's SmPC for both IMPs. Copies of these should be maintained in the Investigator Site File and Pharmacy Site File at the site.

Trial specific SPCs for both IMPs will also be provided in the Investigator Site File and Pharmacy Site File Investigator Site File and Pharmacy Site File at the site and should be used for pharmacovigilance purposes.

12.6 IMP Prescribing

Prescribing of DMARD and prednisolone taper be the responsibility of the site rheumatologist. Results of the most recent available blood monitoring tests must be checked before each new prescription of MTX and continuation of the taper schedule is issued and found to be acceptable relative to the parameters listed in section 13.4.1.

The prescriber should specify the day of intake on the prescription. Prescriptions will be sent to the local site pharmacy for dispensing. As the IMPs are generic hospital stocks being prescribed 'off-label' no trial-specific prescription is required. sites will use their local standard prescriptions. A note of the location of completed prescriptions should be stored in the Pharmacy Site File.

Where the site uses electronic prescribing programmes the pharmacy must provide verification that checks of the prescribing programmes have been made to ensure that the regimen is correct and authorised by the investigator or delegate.

12.7 IMP Labelling

As the IMPs are marketed within the UK but will be used outside their marketing authorisation additional labelling in line with Directive 2001/20/EC and the Medicines for Human Use (Clinical Trials) Regulations 2004 (amended 2006) will be applied. The labelling will include the following:

- 'For clinical trial use only'
- Trial Name: STERLING trial
- EudraCT number: 2023-000130-15
- Participant Trial ID

site pharmacies will be responsible for applying the labels to both MTX and LEF.

Participants will be issued with a Trial ID card by the rheumatology team at the time of STERLING trial randomisation. This will detail:

- The name of the trial
- Participant name
- Participant trial number
- the Investigator name and telephone numbers to contact in a medical emergency
- Sponsor name and contact details
- IMP allocation (a new card will be issued for participants who transfer from MTX to LEF)
- A request to notify the research team if the participant is admitted to hospital in order to monitor SAEs fulfilling this definition

12.8 IMP Dispensing

Where the participant is randomised to the Usual Care plus DMARD arm, the site pharmacy will receive a STERLING trial Participant Randomisation notification following randomisation. The participant ID log must be updated accordingly.

Upon receipt of the prescription from the rheumatology team, the site pharmacy will then be responsible for dispensing an initial 6-week supply of MTX and folic acid directly to the participant at the end of their baseline appointment. This should ensure the participant has adequate supplies until the next supply.

Subsequent supplies will be posted to participants at home by the site pharmacy. In order to avoid issuing excessive supplies of MTX it is advised that the second dispensing should contain a 2-month supply of MTX, and subsequent dispensing contain 3 months' worth of MTX. However, amounts can be varied in accordance with the participants' requirements e.g. should a participant be planning a holiday and requires that adequate amounts are dispensed to cover this period.

A copy of any trial specific dispensing instructions must be retained in the relevant section of the PSF (or a statement of its location) and should be available upon request. Sites are responsible for the development and accuracy of any additional process documents that they produce.

Sites will issue trial participants allocated to the DMARD arm with 2.5mg tablets of MTX and not 10mg tablets.

12.9 IMP Accountability

No trial-specific accountability logs are required. Dispensing records will be in line with local standard practice and as a minimum will ensure that IMP is fully traceable by batch number.

Treatment compliance is recorded by the Research Nurse on the Case Report Form; there is no requirement for compliance checks or routine monitoring to be performed within pharmacy.

The trial pharmacist will sign a document to confirm that local hospital systems are in place to cover drug ordering, drug receipt, drug storage and dispensing, and will enable accurate traceability of all drugs used in the trial.

Unused, used or partially used stocks of IMP should be disposed of at site according to local policy.

12.10 Non-IMPs

Within the trial, the following are classed as Non-Investigational Medicinal Product (NIMPs):

- **Folic acid (FA)**

Composition: Oral tablets containing 5mg of folic acid, usually prescribed at the same time as prescribing MTX. It is not necessary to prescribe folic acid alongside LEF. Generic 'off the shelf' site supplies will be used. There is no requirement to ring-fence folic acid for the STERLING trial.

13 TREATMENT

Participants enter the trial already receiving usual care (steroid therapy). Treatment prior to randomisation is not considered part of this clinical trial.

Following randomisation treatment within the trial is:

- **Arm A (Usual Care):** Those randomised to usual care alone continue to receive usual care, anticipated to include steroid therapy.

or

- **Arm B (Usual Care plus DMARD):** Those randomised to usual care plus DMARD continue to receive usual care, anticipated to include steroid therapy.. In addition, they will commence **weekly** oral MTX therapy under the management of the rheumatology team. Folic acid is also prescribed at the same time as oral MTX.

If MTX is not tolerated this may be switched to the second-line DMARD, LEF (see section 13.2).

13.1 METHOTREXATE (MTX) REGIMEN

13.1.1 Methotrexate Pre-treatment Investigations

During screening participants will have undergone a number of assessments in order to assess their suitability/fitness to receive MTX. Please see section 14.4 for details.

13.1.2 Ongoing Blood monitoring during methotrexate therapy

Blood monitoring of methotrexate will follow local recommendations. As a guide the British Society for Rheumatology DMARD monitoring guidelines recommend FBC, U+E and LFT approximately 8ml taken each draw:

- every two weeks until on stable dose for six weeks
- then monthly for three months and
- quarterly thereafter

The site team will issue sufficient laboratory request forms to cover the duration of each prescription and will check the results of the monitoring blood tests before each new prescription of MTX is issued. Providing the results of the prior test do not fall within the limits referred to in section 13.4.1 and are acceptable according to local physician discretion, windows either side of these blood monitoring dates will be allowed. Please see Schedule of Events for details of appropriate windows.

13.1.3 Rules for concomitant therapy in participants receiving methotrexate

All treatments being taken by the participants on entry to the trial or at any time during the trial in addition to the investigational medicinal product are regarded as concomitant treatments and must be documented in the participant's hospital notes; only concomitant treatments relevant to this trial will be recorded on the eCRF as required.

Concomitant medications felt to be clinically indicated would be allowed during the study so long as they do not interfere with the investigational medicinal products (please refer to the applicable SmPC/IB).

Many drug interactions noted in SmPCs relate principally to high-dose MTX, rather than the low-dose MTX used in STERLING and in standard rheumatology practice. Clinicians should review the current DMARD being prescribed and use clinical judgement when initiating any new therapies known to interact with MTX, taking into account whether the interaction is clinically significant for MTX at the dose being used.

13.1.4 Use of Folic Acid during MTX therapy

The administration of folic acid appears to ameliorate side-effects of MTX. Therefore, trial participants prescribed oral weekly MTX must be also prescribed 5mg folic acid at least once per week but up to six days per week. This must **not** be taken on the same day of the week that MTX is taken.

The dose of folic acid remains the same (5mg up to six days per week) for participants receiving MTX, regardless of the MTX dose.

13.1.5 Use of antibiotics during MTX therapy

MTX should never be co-administered with trimethoprim-sulfamethoxazole due (also both folate antagonists) to cytopenia risk.

MTX may be given alongside long-term antibiotics (except trimethoprim-sulfamethoxazole) in some situations, for example long-term prophylactic antibiotics. The site will include a request in the GP letter requesting that should the GP initiate a long-term course of antibiotics the site investigator should be informed in writing.

In the event of an acute infection requiring antibiotic therapy MTX may need to be omitted until the infection has resolved and the antibiotics have stopped. Please see Section on MTX Delays and Dose Modifications below for further detail (section 13.1.16)

Participants will be advised to provide any clinician with their Participant ID card to inform them that they are participating in the study which will advise that they are taking a DMARD. The card will also instruct participants to contact the site research team if they are prescribed antibiotics so appropriate advice can be given.

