7.5.2 Potential for drug interactions

The PI will be responsible for prescribing DMARD. At the time the DMARD is initiated, the PI will check for relevant interactions of the DMARD with any concomitant medications. They will also communicate any starting or stopping of DMARD with the participants GP in a timely fashion.

DMARD should normally be paused (temporarily stopped) during a course of antibiotics that might be prescribed for intercurrent infection. For mild, uncomplicated infections in the community that have resolved by the end of

the course of antibiotics, and where broad-spectrum antibiotics have not been used, DMARD can generally be restarted after the antibiotics have finished. However, if there is any doubt, the participant and/or GP may contact the site for advice on when to restart the DMARD after completion of the course of antibiotics, depending on the infection type or severity, or if there are any other queries in relation to intercurrent infection.

MTX may accumulate in renal impairment. If acute deterioration in renal function occurs in a participant being prescribed MTX during the study, and the participant is in the community, GPs are asked via the trial specific GP letter to notify the site of this so that the MTX can be stopped, paused or dose-reduced by the site as necessary. If the participant is admitted to hospital then the admitting team will be at liberty to manage MTX dosing as clinically indicated in consultation with the rheumatology team.

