4. A medical condition other than PMR that has required >2 courses of systemic glucocorticoid treatment lasting 5 days or more, or any course lasting 30 days or more, during the year prior to randomization.
5. Giant cell arteritis (previous or current) in the opinion of the local investigator.
6. Rheumatoid arthritis, psoriatic arthritis or spondyloarthritis (previous or current) in the opinion of the local investigator
7. At the baseline visit active infection of sufficient severity to be a contra-indication to commencing methotrexate, in the opinion of the local investigator.
8. Participant taking concurrent trimethoprim-sulfamethoxazole at the time of the baseline assessments
9. Active gastric ulcer at the baseline visit in the opinion of the local investigator
10. Known prior history of a significant immunodeficiency syndrome, defined as an immunodeficiency severe enough to cause recurrent infections of frequency or severity that in the opinion of the investigator would preclude DMARD treatment
11. Known prior history of hereditary galactose intolerance, hereditary total lactase deficiency or hereditary disorder of glucose-galactose malabsorption
12. Current treatment with folate antagonists including trimethoprim-sulfamethoxazole
13. Other medical condition that in the opinion of the local investigator is severe enough to seriously compromise evaluation of the primary or key secondary endpoints
14. Treatment with any immunosuppressive therapy (conventional synthetic, targeted synthetic or biological DMARD) within 3 months prior to randomisation.
15. Treatment with any investigational drug in the last 4 months prior to the start of protocol treatment.
16. Unable to complete essential study procedures and communicate with study staff independently.
17. Participants must NOT fulfil any of the following within 6 weeks prior to baseline: Haemoglobin <10.0 g/dL; total white cell count <3.5 x10⁹/L; absolute neutrophil count <1.5 x10⁹/L; platelet count <100 x10⁹; ALT (alanine aminotransferase) or AST > 2 x upper limit of reference range for the laboratory conducting the test, eGFR (estimated glomerular filtration rate) <30ml/min

18. Evidence of respiratory disease on chest radiograph (performed during screening or within the 6 months prior to screening) of sufficient severity to be a contra-indication to commencing methotrexate, in the opinion of the local investigator.

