DMARD Use Review if applicable			x	x	x	x	x	x		
Medical History		x	x	x	x	x	x			
AEs/SAEs review			x	x	x	x	x	x		
Chest X-Ray*	x									
Pregnancy Test	x									
RF [§]	x									
ACPA [§]	x									
U&E	x	x	x	x	x	x	x		x	
FBC	x	x	x	x	x	x	x		x	
Liver Function Test	x	x	x	x	x	x	x		x	
HbA1C		x	x	x	x	x	x			
CRP (Also needed for PMR-AS)	x	x	x	x	x	x	x			
ESR		x	x	x	x	x	x			
Physical Examination	x	x	x	x	x	x	x			
Vital Signs	x	x	x	x	x	x	x			
PMR Activity Score		x	x	x	x	x	x			
(PMR-AS) Number of minutes of morning stiffness		x		x				x		
(PMR-AS) Upper limb elevation / active shoulder abduction		x		x				x		
(PMR-AS) VAS global assessment (physician)		x		x				x		

Steroid Free Remission								x		
------------------------	--	--	--	--	--	--	--	---	--	--

* a report from a chest x-ray performed within the 6 months prior to the screening visit is acceptable to confirm eligibility providing that no evidence of interstitial lung disease or tuberculosis or active.

† As a guide the British Society for Rheumatology DMARD monitoring guidelines recommend FBC, U+E and LFT: every two weeks until on stable dose for six weeks, then monthly for three months and quarterly thereafter. Blood pressure should be measured at the same timepoints as these blood tests.

‡ Providing the results of the prior test are acceptable (see section 13.4.1), a window will be allowed one week either side of the scheduled date during the first six weeks, two weeks either side of the next scheduled date for the next three months and one month either side of the next scheduled date thereafter

§ Rheumatoid factor (RF) and anti-citrullinated peptide antibody (ACPA/anti-CCP) both within local laboratory reference range at or within the 12 months prior to the screening visit

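### Folate antagonists are barred as a class at entry (exclusion 12), but section 13.1.5 expressly prohibits only trimethoprim-sulfamethoxazole once methotrexate is being taken

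*Protocol*

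**What the plan says.** Two eligibility items in Protocol section 8.2 bear on this. Exclusion 8 names one product: "Participant taking concurrent trimethoprim-sulfamethoxazole at the time of the baseline assessments". Exclusion 12 names a class: "Current treatment with folate antagonists including trimethoprim-sulfamethoxazole". Section 8 allows no eligibility waivers.

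For participants on MTX, section 13.1.5 opens with an absolute rule: "MTX should never be co-administered with trimethoprim-sulfamethoxazole due (also both folate antagonists) to cytopenia risk". It then gives a qualified permission: "MTX may be given alongside long-term antibiotics (except trimethoprim-sulfamethoxazole) in some situations, for example long-term prophylactic antibiotics". The GP letter asks to be told in writing of any long-term antibiotic course. The section ends with the ID card: "The card will also instruct participants to contact the site research team if they are prescribed antibiotics so appropriate advice can be given".

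Three other places govern drugs taken alongside MTX:

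- Section 13.1.3 allows clinically indicated drugs provided they do not interfere with the trial drugs, and refers to the SmPC. It adds that many listed interactions relate mainly to high-dose MTX, and asks clinicians to "use clinical judgement when initiating any new therapies known to interact with MTX".
- Section 7.5.2 covers acute infection: "DMARD should normally be paused (temporarily stopped) during a course of antibiotics that might be prescribed for intercurrent infection".
- Section 13.1.17 likewise has MTX omitted during antibiotics for an acute infection.

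**The concern.** The reason given in 13.1.5 applies to any folate antagonist, but the ban that follows covers one combination product. The next sentence makes that product the only named exception to the allowance for long-term antibiotics. The on-treatment rule is therefore narrower than the entry rule and narrower than its own stated reason.

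The difference also runs in the wrong direction. The entry bar applies to everyone, including those later allocated to usual care alone. The on-treatment rule applies only to people actually exposed to the combination of drugs, so it should be at least as strict.

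What is at stake is a site's answer to a practical question. If a GP or participant reports a new long-term antibiotic, the obvious place to look is 13.1.5, which is headed for that purpose. It names one product and not the class. The protocol puts the average age at PMR onset at around 75, admits patients with eGFR down to 30 ml/min, notes that MTX may accumulate in renal impairment, and permits up to 25 mg weekly. An explicit instruction is worth having in that population.

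**Working it through.** There is no figure in the plan to reproduce; the check is a comparison of rules.

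**1. Scope of each rule**

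| Rule | Applies to | What it bars |
|---|---|---|
| Exclusion 8 | Everyone at baseline | Trimethoprim-sulfamethoxazole |
| Exclusion 12 | Everyone at entry | Folate antagonists as a class |
| 13.1.5, first sentence | Participants on MTX | Trimethoprim-sulfamethoxazole |
| 13.1.5, long-term antibiotics | Participants on MTX | Trimethoprim-sulfamethoxazole, as the only named exception to a qualified permission |

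Exclusion 8 already covers the combination, so exclusion 12 adds substance only if it reaches further. The reading of exclusion 12 as a class rule does not depend on the word *including* alone.

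**2. Does another on-treatment rule restore the class bar?**

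- *13.1.3:* a general non-interference condition, with interacting drugs left to judgement. It states no class prohibition.
- *GP letter and ID card:* these prompt notification and contact. As described in the protocol, they do not prohibit anything.
- *7.5.2 and 13.1.17:* MTX is paused for acute courses. This largely closes the gap for acute treatment but not for long-term or prophylactic use, which is the case 13.1.5 expressly allows.
- *Blood monitoring:* this detects a cytopenia only after it has occurred.

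**3. How often would monitoring look?**

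This is context for the last item, assuming sites follow the guide schedule in 13.1.2: two-weekly until the dose has been stable for 6 weeks, monthly for 3 months (13 weeks), then quarterly. Weeks are counted from the start of MTX.

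Start of quarterly phase = week of last dose change + 6 + 13:

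- no dose change: 0 + 6 + 13 = week 19
- last escalation at week 4: 4 + 6 + 13 = week 23
- last escalation at week 26: 26 + 6 + 13 = week 45

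Quarterly interval = 3 × 52/12 = 13.0 weeks. In this phase the footnote to section 14.2 allows a window of "one month either side of the next scheduled date thereafter", provided the previous result was acceptable. With one test on time and the next a month late, the interval is 4 × 52/12 = 17.3 weeks.

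Study-visit blood counts at weeks 12, 24, 36 and 48 shorten these intervals up to week 48. The next study-visit count is at week 80, so between those visits the local schedule is the only backstop. Section 12.6 requires results to be checked before each new prescription, but section 12.8 advises three-month supplies from the third dispensing, so that check is also roughly quarterly.

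**The case against.** The best case for leaving the text alone is that 13.1.3 already governs the matter. It is a condition on every drug taken with MTX, it points to the SmPC, and the more specific 13.1.5 does not switch it off. 13.1.5 says only that MTX may be continued, and only in some situations. One absolute ban plus clinical judgement for everything else is a coherent design. Entry and on-treatment rules need not match, because a prescriber can pause, reduce or stop MTX once treatment has begun. The documents name no folate-antagonist antibiotic other than the combination, and the texts of the GP letter, the ID card and the SmPC are not shown.

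Much of this stands as a limit on weight. Use is discretionary, not uncontrolled. Trimethoprim alone is my example and not the protocol's. The letter or card may already carry the class wording. The monitoring intervals describe the backstop and do not measure the gap; they depend on sites using the guide schedule, whereas 13.1.2 lets local recommendations prevail.

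It does not remove the inconsistency. 13.1.3 tells clinicians that many listed interactions matter mainly at high MTX doses and then leaves the decision to them. A reader could use that to discount the very interaction exclusion 12 treats as disqualifying. The sentence giving the reason in 13.1.5 is garbled, but on either reading of its parenthesis (MTX and the combination, or the combination's two components) the reason remains folate antagonism with cytopenia risk.

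**Conclusion.** The point holds. The entry rule covers a class, the express on-treatment prohibition covers one product, and the reason given for the prohibition applies to the class. No other on-treatment rule in the protocol states the class bar.

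The practical gap is mainly long-term or prophylactic use of a folate antagonist other than the named combination, and it exists only while a participant is taking MTX, not after stopping or switching to leflunomide. Its frequency cannot be estimated from the documents. If it occurred in the quarterly phase, blood counts could be about 13 to 17 weeks apart under the assumptions above, and less up to week 48 because of study visits.

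This is a participant-safety wording fault that should be corrected. It has no bearing on the primary analysis or power.

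**What to change.** In section 13.1.5, replace the single product name in both sentences (the absolute ban and the exception to the long-term antibiotic allowance) with: *other folate antagonists, including trimethoprim alone and trimethoprim-sulfamethoxazole*. The sponsor's clinical team should confirm the named members. The word *other* is there because MTX is itself a folate antagonist. The garbled parenthesis in the first sentence can be tidied at the same time.

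Then check that the GP letter and the participant ID card carry the same wording; if they already do, they need no change. Merging exclusion 8 into exclusion 12 would be tidier but is optional.

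The cost is two edited sentences and a check of two participant-level documents. No new procedures, visits or data are needed.
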